6.3. Multi-Center Studies

Sites will not be pooled for any inferential analysis or descriptive summary in this study.

6.4. Multiple Comparisons / Multiplicity

No multiplicity adjustment will be applied in this study. Treatment differences in IOP between DE-117 QD arm and DE-117 BID arm for each timepoint will be considered statistically significant if the *p*-value of the corresponding treatment comparison is smaller than 0.05. Superiority of DE-117 BID to DE-117 QD is achieved if the treatment differences are significantly greater than 0 at all six time points.

6.5. Interim Analysis

No interim analysis is planned for this study.

7. SUMMARY OF STUDY POPULATION DATA

7.1. Subject Disposition

The disposition of all randomized subjects will be summarized by treatment and overall. The summary will include the number of subjects in the FAS population and the numbers and percentages of subjects in the other study populations including the Safety population, and the PPS population. The disposition summary will also include the number and percentage of completers and non-completers at Week 6 (Visit 4), respectively, as well as the number and percentage of non-completers at Week 6 (Visit 4) by the primary discontinuation reason from the study drug and from the study.

7.2. Demographics and Baseline Characteristics

Subject demographics and baseline characteristics will be descriptively summarized for the FAS population by planned treatment, Safety population by actual treatment, and overall. Specifically, for subject demographics, the following variables will be summarized:

- Age at randomization (continuous and categorical: < 65 years or \geq 65 years)
- Sex (categorical: Male or Female)
- Ethnicity (categorical: Hispanic/Latino or Not)
- Race (categorical: American Indian or Alaska Native, Asian, Black or African American, Native Hawaiian or Other Pacific Islander, White, or Other)

For baseline characteristics, the following variables will be summarized for study eye:

- Primary ocular diagnosis (categorical: POAG, or OHT)
- Prior use of Prostaglandin analogs (Yes or No)
- Baseline mean diurnal IOP score and baseline IOP score at each scheduled timepoint (08:00, 12:00, and 16:00)

- Visual acuity
- Glaucomatous optic nerve findings (categorical: none, mild, moderate, or severe)

7.3. Medical and Surgical History

For this study, medical and surgical history will be coded using MedDRA 21.1, 2018. Each medical event will be classified into a SOC and mapped to a PT.

The medical and surgical history will be summarized for the FAS population. Subjects reporting any medical and surgical history at baseline will be tabulated by SOC and PT for each planned treatment and overall.

7.4. Protocol Deviations

In this study, protocol deviations are categorized as follows:

- Informed Consent
- Inclusion/Exclusion Criteria
- Concomitant Treatment
- Investigational Product
- Procedures/Tests/Assessments/ Laboratory
- Safety Reporting
- Time Window
- Withdrawal Criteria
- Other deviations

A protocol deviation is considered major if it may affect the subject's rights, safety, or well-being and/or the completeness, accuracy, and reliability of the study data. Santen's study team will review all protocol deviations and determine the list of major protocol deviations prior to database lock. All randomized subjects with any major protocol deviation(s) will be tabulated by deviation category for each planned treatment and overall. In addition, protocol deviations will also be listed.

7.5. Prior and Concomitant Medications

For this study, non-study medications, including prior and concomitant medications, will be coded using World Health Organization Drug Dictionary Enhanced (WHO-DDE) (March 2017). Each non-study medication will be classified using the Anatomical-Therapeutic-Chemical (ATC) classification system and mapped to a WHO-DDE preferred drug name.

Non-study medications will be summarized for the Safety population. Subjects taking any prior medications will be tabulated by ATC level 3, level 4 and preferred drug name for each actual treatment received and overall. A subject will be counted at most once for each prior medication, even if the subject took the same prior medication on multiple occasions. Subjects

taking any concomitant medications will be tabulated similarly. In addition, prior medications and concomitant medications will also be listed, separately.

7.6. Treatment Compliance

A subject will be considered fully compliant to treatment if the he/she responded “0” at all post-baseline visits to the eCRF question “How many doses were missed since the previous visit?”

The treatment compliance rate for a subject at a visit will be as following:

- Compliance Rate (%) = $(2 * \text{Duration} - \sum \text{Miss}) / (2 * \text{Duration}) \times 100$

Where:

Duration: The number of days subject should have administered study medication, calculated as treatment end date – Baseline date.

Miss: The number of missed doses since the last visit day(s)

For subjects in the FAS, the compliance rate will be summarized by post-baseline analysis visit for each planned treatment.

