6.4. Study Intervention Compliance

To obtain reliable safety and efficacy data, the following precautions will be taken to ensure compliance with the treatment regimen during the study:

- Subjects will receive verbal and written instructions for proper instillation of the study medication, the dosing regimen, and the conditions of the study medication storage.
- Subjects will be reminded at study visits to consistently dose in each eye at the same time of the day.

- Twice daily at 20:00 and 8:00 [± 60 min] through Visit 2 to 4.
- Subjects will be reminded of the morning and evening instillation of the study drug on the day prior to Visit 3 (Week 2) and Visit 4 (Week 6)/Early Termination respectfully.
- Subjects will be reminded that the morning instillation of the study drug at Visit 3 (Week 2) and Visit 4 (Week 6)/Early Termination will be done at the clinic.
- Since subjects must have a diagnosis of POAG or OHT in both eyes, both eyes should be treated for the duration of the study, even if only one eye is eligible per IOP inclusion criteria.
- Subjects will be queried regarding compliance with the protocol's dosing regimen at Visit 3 (Week 2) and Visit 4 (Week 6)/Early Termination.
- Subjects will be counseled on proper dosing procedures and dosing schedule if the subject's compliance is not 100%. If a subject deviates from the prescribed dosage regimen, the specific dates of the missed doses should be recorded.
- A subject's dosing compliance for a specific period is determined by the total number of days that subject followed the proper dosing procedures and dosing schedule. Stoppage of study medication use, overdosing of study medication, incorrect time (outside of protocol-specified time point ± 60 min) of study medication administration, will be noted as non-compliance. The subject's dosing compliance will be recorded in the subject's source documents and on the eCRF at Visit 3 (Week 2) and Visit 4 (Week 6)/Early Termination.
- Subjects may be discontinued from the study at the discretion of the Investigator if the subject cannot be brought into compliance.

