4.1.2. Treatment Start and End Dates

Treatment start date is the date at which a randomized subject takes the first dose of the study medication.

Treatment end date is the date at which a randomized subject takes the last dose of the study medication. If the date of the last dose is missing, then

- The day before the Visit 4 (Week 6) will be considered the treatment end date for subjects who completed the study, and
- The day before the Exit Visit date will be used for subjects who prematurely discontinued from the study. If the Exit Visit date of a non-completer is not available, then the day before the last available visit date will be considered the treatment end date.

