4.1.4. Out-of-Window Measurements, Analysis Visit, and Analysis Window

Analysis visit is a timing variable to be used for analyses involving visits. For each analysis visit, an *analysis window* is set up to determine the analysis visit to which a measurement should be mapped ([Table 3](#)).

The analysis visit of a measurement will be determined based on the study day of the measurement and specified analysis windows and is not necessarily the same as the study visit at which the measurement was collected. For example, an out-of-window measurement collected at the Week 2 study visit will be mapped to the Week 6 analysis visit, if the study day of the measurement falls into the analysis window of Week 6.

Table 3: Analysis Visit and Analysis Window

| Analysis Visit (Target Assessment Date) | Protocol Visit Window | Analysis Window |
|---|-----------------------|-----------------|
| Baseline (Day 1) | [1, 1] | - 1] |
| Week 2 (Day 15) | [13, 17] | [2, 28] |
| Week 6 (Day 43) | [40, 46] | [29, 57] |

In case that there are two or more visits that fall into the same analysis window, then the visit closest to the target assessment day will be selected for that visit window. In the case that two visits are equidistant to the target assessment day, i.e., one is before and one is after the target assessment day, the later one will be selected for that visit.

For analyses of IOP involving post-baseline visits, if there are two or more visits that fall into the same analysis window of a post-baseline visit, then the visit in which IOP are measured at all the scheduled timepoints (8:00, 12:00, and 16:00) will be selected for that analysis visit first, before applying the above rule.

Furthermore, if applying this analysis window results in missing IOP data, then the nominal visit will be used.

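### SAP 7.6 divides doses missed by Week 2 by the doses due over the whole treatment period, so Week 2 compliance is overstated for subjects who go on dosing

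*SAP*

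**What the plan says.** SAP 7.6 introduces the formula with the words "The treatment compliance rate for a subject at a visit will be as following" and ends by stating, for the FAS, that "the compliance rate will be summarized by post-baseline analysis visit for each planned treatment". The rate is 100 × (2 × Duration − sum of Miss) / (2 × Duration). Duration is "The number of days subject should have administered study medication, calculated as treatment end date" minus the Baseline date. Miss is the count of doses missed since the previous visit.

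SAP 4.1.2 says that the treatment end date "is the date at which a randomized subject takes the last dose of the study medication". That is one date per subject, not one per visit, and no other section supplies a visit-specific Duration. SAP 7.6 also calls a subject fully compliant if zero missed doses are reported at every post-baseline visit.

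Protocol 6.4 takes a different unit. It judges compliance over a given period by the number of days on which dosing was done properly and on schedule. It says that stoppage, overdosing and an incorrect time (more than 60 minutes off) "of study medication administration, will be noted as non-compliance".

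**The concern.** At Week 2 the numerator and the denominator cover different spans. The misses come from about two weeks of dosing, while the doses due come from the whole study, including four weeks that have not yet happened. The Week 2 rate is then too high for anyone who continues treatment and missed at least one dose.

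The two arms differ only in whether the 08:00 drop is active or vehicle, so adherence is the natural context for reading a difference between BID and QD, or the lack of one. Week 2 also supplies three of the six primary time points. A Week 2 table built as written would make adherence look better than it was. Among on-schedule completers, it would also shrink any between-arm difference in missed doses to about a third of its size.

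**Working it through.** The documents state no compliance figure, so there is nothing to reproduce. The check applies the SAP formula and compares it with the same formula taken only to the visit.

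**Inputs**
- Two drops per eye-day in both arms, 20:00 and 08:00 (Protocol 6.2.2, 6.4). The first dose is on the evening of Day 1 (Protocol 4.1).
- Week 2 is Day 15 (13 to 17) and Week 6 is Day 43 (40 to 46) (SAP 4.1.4, Table 3).
- The morning dose on visit days is given in clinic (Protocol 8.1.4, 8.1.5).

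**Doses due**
- To the Day 43 morning dose: 1 + 41 × 2 + 1 = 84 = 2 × (43 − 1). The SAP denominator is right for the whole period.
- To the Day 15 morning dose: 1 + 13 × 2 + 1 = 28 = 2 × (15 − 1).

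**Week 2 rate, subject who completes on schedule**

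| Missed by Week 2 | SAP 7.6: (84 − m)/84 | To the visit: (28 − m)/28 | Overstatement (points) |
|---|---|---|---|
| 0 | 100% | 100% | 0 |
| 1 | 98.8% | 96.4% | 2.4 |
| 7 | 91.7% | 75.0% | 16.7 |
| 14 | 83.3% | 50.0% | 33.3 |

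The shortfall from 100% is divided by 84/28 = 3.0.

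**Range over the visit windows**
- Visit 3 on Day 17, last dose on Day 40: 39/16 = 2.4.
- Visit 3 on Day 13, last dose on Day 46: 45/12 = 3.75.
- If the last-dose date is missing, SAP 4.1.2 uses the day before Visit 4 for a completer. Duration is then 41 days and the factor is 82/28 = 2.9.

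**Mixed scales.** A subject whose last dose is on Day 15 has Duration 14. With 7 missed, the SAP rate is (28 − 7)/28 = 75.0%, which is correct. A completer with the same 7 missed by Week 2 shows 91.7% in the same column.

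**Does another reading of the sum rescue it?** Suppose 7 doses are missed by Week 2 and 7 more by Week 6.
- Sum taken cumulatively to each visit: Week 6 is (84 − 14)/84 = 83.3%, which is correct. Week 2 stays wrong.
- Only misses since the previous visit: Week 6 is (84 − 7)/84 = 91.7%, against (56 − 7)/56 = 87.5% of the 56 doses due between Day 15 and Day 43. Both visits are overstated.
- All misses in the study at every visit: the Week 2 and Week 6 rates are identical, and a table by visit has no meaning.

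**The case against.** The best defence is that little hangs on this table. The rate enters no model and no success rule. Both arms instil two drops a day, so the formula favours neither regimen. The size depends wholly on how many doses are missed. The missed-dose counts and the fully compliant flag do not use the denominator. With cumulative counting, early misses reappear correctly in the Week 6 rate. All of this stands. It limits the consequence but does not make the Week 2 number right.

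A reader might infer more than the documents support:
- **That the error distorts the per-protocol set.** SAP 5.4 bases exclusion on review of protocol deviations and SAP 7.4 describes how deviations are reviewed. Neither refers to this rate or to a cut-off. Dates of missed doses are recorded separately (Protocol 6.4).
- **That subjects would be wrongly passed at a threshold such as 80%.** The documents set no compliance threshold.
- **That a subject who took nothing would still show about two-thirds compliance at Week 2.** The Day 15 morning dose is given in clinic, with staff making sure that it is instilled (Protocol 8.1.4), so that extreme is not realistic. Compliance is also listed before that dose in the visit order. If it is queried then, 27 doses have fallen due instead of 28, which barely alters the figures.
- **That leaving out mistimed and extra doses is a calculation error.** It is a narrower measure. Protocol section 9 specifies no compliance analysis and leaves detail to the SAP. Such events can also surface as listed protocol deviations (SAP 7.4) or, if significant administration errors, as listed events of special interest (SAP 9.1).

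**Conclusion.** The point holds for the by-visit denominator. As written, the Week 2 rate is wrong for every subject who misses a dose by then and continues treatment. The error is small with few misses and large with many. Week 6 is also overstated if its sum covers only the interval since Visit 3. This rests on the literal definition of treatment end date, on misses being those reported up to the visit, and on subjects completing within the visit windows. No statement can be made about the error in the actual data, because it depends on the missed-dose counts.

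The consequence is confined to a descriptive table, but the table would be reported as defined and the correction is cheap, so it should be made.

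A secondary point stands in a modest form. A subject who took every dose at the wrong time would score 100% and fully compliant under SAP 7.6, while Protocol 6.4 would note non-compliance. The two documents use the same word for different things.

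**What to change.** Make Duration specific to the visit and match Miss to the same span. Either version works, provided the SAP names it:
- **Cumulative rate:** doses due = 2 × (the earlier of visit date and treatment end date, minus Baseline date), with misses summed since Baseline.
- **Interval rate:** doses due = 2 × (the earlier of visit date and treatment end date, minus previous visit date), with misses over that interval. If this is zero or negative, no dose was due and no rate is calculated.

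The cap at treatment end is needed because Protocol 7.1 encourages subjects who stop study drug to stay for the remaining visits. Without the cap, doses would count as due after dosing had ended. Keep the whole-period formula only for one overall rate per subject.

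For the secondary point, label the SAP measure and flag as missed-dose compliance, or reconcile them with Protocol 6.4 if the eCRF fields allow. The only eCRF compliance question that the SAP cites is the number of missed doses, so the sponsor should first confirm whether timing and extra doses are captured in a form that can be analysed.

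The cost is a sentence or two in the SAP and minor programming, with no new visits or subjects. Reported Week 2 compliance will be less favourable.

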7.7. Exposure to Study Medication

The duration of exposure to a study medication is measured by days on treatment as derived in [Section 4.1.3](#). For subjects in the Safety Population, the duration of exposure will be summarized using descriptive statistics, and frequency and percentage of subjects will be tabulated by duration category (1-14 days, 15-28 days, or > 28 days) for each actual treatment received.

8. EFFICACY ANALYSES

Unless specified otherwise, the efficacy analyses will be performed on the FAS, where subjects are classified by planned treatment, irrespective of the actual treatment received.

Unless specified otherwise, all efficacy analyses will be performed on the study eye, and the data on fellow eye will not be used.

8.1. Analyses of Primary Endpoint

8.1.1. Primary Analyses

The primary efficacy endpoint is IOP in the study eye at each scheduled timepoint (08:00, 12:00 and 16:00) at Weeks 2 and 6 (Visits 3 and 4). The comparison between DE-117 BID arm and QD arm will be performed with the following hypotheses:

$$H_{0i}: \mu_{Bi} = \mu_{Qi}$$

versus

$$H_{1i}: \mu_{Bi} \neq \mu_{Qi}$$

where μ_B and μ_Q denote the mean values of the primary endpoint in DE-117 BID arm and QD arm at $i = 1, 2, \dots, 6$ timepoints, with $i = 1, 2, 3$ represent 08:00, 12:00 and 16:00 at Week 2 and $i = 4, 5, 6$ represent 08:00, 12:00 and 16:00 at Week 6, respectively.

The primary analyses will be performed on the FAS. A mixed-effect model for repeated measures (MMRM) will be carried out for each timepoint. Each model will include treatment, visit, and treatment-by-visit interaction as fixed effects, baseline IOP as a covariate. Within-subject errors will be modeled using an unstructured covariance matrix. Least squares mean of the endpoint within each treatment arm will be reported. The 95% confidence intervals (CIs) for the difference in means between DE-117 BID arm and QD arm at each timepoint and the corresponding p-values will be provided.

If the model with unstructured covariance matrix fails to converge, the following structures other than unstructured are to be used in order of 1) heterogeneous toeplitz (TOEPh), 2) heterogeneous autoregressive of order 1 (ARH(1)), 3) heterogeneous compound symmetry (CSH), 4) compound symmetry (CS) and the first (co)variance structure that converges would be used as the primary analysis.

8.1.2. Sensitivity Analyses

To assess the robustness of the results from the primary analysis for primary endpoint, the sensitivity analysis will be performed using the same MMRM model on PPS. All the primary and sensitivity analyses will be implemented using SAS PROC MIXED. The main part of the SAS code for the specified MMRM analysis is provided in [Appendix 12.1](#).

8.2. Analyses of Secondary Endpoints

For continuous secondary endpoints (mean diurnal IOP, change and percent change from baseline) at Week 2 (Visit 3) and Week 6 (Visit 4), MMRM and descriptive summaries will be performed. The MMRM will be the same as the one for primary endpoint.

For binary secondary endpoints, the responder rates will be summarized at each post-baseline visit. Pearson's Chi-square test will be used for comparison between DE-117 BID arm and QD arm.

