9.3.6.1. Analysis of Primary Endpoint

The primary efficacy endpoint is IOP in the study eye at each specified timepoint (08:00, 12:00 and 16:00) at Week 2 (Visit 3) and Week 6 (Visit 4). For the primary analysis, a mixed-effect model for repeated measures (MMRM) will be carried out and least squares mean of the endpoint will be reported. The model will include treatment, visit, and treatment-by-visit interaction as fixed effects, baseline IOP as a covariate, and subject as a random effect.

Treatment differences between the DE-117 BID arm and QD arm will be reported for each time point along with p-values and 95% confidence intervals.

Analysis of covariance (ANCOVA) with missing data imputed by an LOCF approach will be used as sensitivity analyses.

In addition, plots of IOP measures versus analysis time/analysis visit will be provided.

9.3.6.2. Analysis of Secondary Efficacy Endpoints:

- Mean diurnal IOP in the study eye at Week 6 (Visit 4)
- Absolute change and percent change from baseline in IOP
- Absolute change and percent change from baseline in mean diurnal IOP
- Having a mean diurnal IOP reduction $\geq 20\%$, $\geq 25\%$, or $\geq 30\%$ from Baseline (Visit 2) at each post-baseline visit
- Having a mean diurnal IOP ≤ 18 mmHg at each post-baseline visit

Continuous secondary efficacy endpoints will be analyzed by a mixed-effects model for repeated measures (MMRM) using observed cases or analysis of covariance (ANCOVA) with missing data imputed by an LOCF approach. Binary secondary efficacy endpoints will be analyzed using Pearson's Chi-square test.

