3.2. Randomization and Masking

A permuted-block randomization will be employed to randomize eligible subjects in a 1:1 ratio to either DE-117 QD/Vehicle QD arm or DE-117 BID arm. The randomization schedule will be generated and implemented using central randomization via Interactive Response Technology (Medidata Balance/RTSM).

Treatment assignments will be masked to Santen, study subjects, and Clinical Investigator. The appearance of the bottles of DE-117 ophthalmic solution 0.002% and the vehicle will be identical. All subjects will receive bottles labeled "morning" for the morning dose and bottles labeled "evening" for the evening dose. Each eligible subject will be assigned to receive a numbered study medication kit as assigned by central randomization via Interactive Response Technology at Visit 2 (Baseline). In case of a medical emergency, the Principal Investigator may reveal the treatment information by unmasking through Medidata Balance/RTSM to know which treatment the subject has received.

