3.3. Sample Size Planning

The sample size calculation does not consider multiplicity from multiple time points. Assuming a two-sided type I error rate of 5% and a standard deviation of 3.5 mmHg, approximately 50 subjects per treatment arm (100 in total) will have about 80% power to detect a 2.0 mmHg between-treatment difference.

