6.1. Adjustments for Covariates

In general, baseline IOP score will be adjusted in the inferential analysis of each IOP endpoint. Detailed information on covariate adjustment is provided in [Section 8.1](#).

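### The ≤18 mmHg responder comparison omits baseline IOP, an unexplained exception to SAP 6.1 that gives up some power; the percent-reduction responders lose almost nothing

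*SAP*

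**What the plan says.** SAP 6.1 sets a general rule: "In general, baseline IOP score will be adjusted in the inferential analysis of each IOP endpoint". It then sends the reader to Section 8.1 for details, and Section 8.1 covers only the primary-endpoint MMRM, which has baseline IOP as a covariate.

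SAP 8.2 applies the same MMRM to the continuous secondary endpoints (mean diurnal IOP, change and percent change). For the binary endpoints it summarises responder rates and says that Pearson's "Chi-square test will be used for comparison between DE-117 BID arm and QD arm". Protocol 9.3.6.2 agrees: "Binary secondary efficacy endpoints will be analyzed using Pearson's Chi-square test".

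SAP 4.2.5 defines four binary endpoints, each assessed at Weeks 2 and 6. Three are reductions in mean diurnal IOP of at least 20%, 25% or 30% from baseline. The fourth is a mean diurnal IOP of 18 mmHg or lower.

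Neither document specifies an adjusted or stratified analysis of these endpoints, gives a reason for treating them differently, or names an effect estimate with a confidence interval for them.

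**The concern.** The SAP analyses mean diurnal IOP with baseline adjustment when it is continuous and without it when it is dichotomised. For ≤18 mmHg this can matter. Protocol inclusion criterion 9 requires the study eye to be between 22 and 34 mmHg at all three baseline times. An eye starting at 22 must fall 4 mmHg (4/22 = 18%) to respond; an eye starting at 34 must fall 16 mmHg (16/34 = 47%). Starting level should therefore predict response. Randomisation is described only as permuted-block, 1:1, with no stratification by baseline IOP.

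At stake is the precision of a secondary comparison in a trial with 50 subjects per arm. The covariate is already collected for every randomised subject.

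**Working it through.** **1. The plan's own figure.** SAP 3.3: two-sided 5%, SD 3.5 mmHg, difference 2.0 mmHg, 50 per arm, about 80% power.
- Standard error of the difference = 3.5 × √(2/50) = 0.70; 2.0/0.70 = 2.857.
- Normal approximation: Φ(2.857 − 1.960) = 81.5%. Noncentral t with 98 df: 80.8%.
- n per arm = 2 × (1.960 + 0.842)² × 3.5²/2.0² = 48.1, so 49.

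The figure reproduces. It concerns the continuous endpoint, and the documents claim no power for the binary ones.

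**2. Chi-square power for ≤18 mmHg, by hand.** The QD mean at follow-up is not in the documents; I assume 18.5 or 20.0 mmHg. With normal data:
- QD 20.0, BID 18.0: p = Φ(−2.0/3.5) = 0.284 and Φ(0) = 0.500. Null SE = √(2 × 0.392 × 0.608/50) = 0.0976; SE under the alternative = √((0.284 × 0.716 + 0.500 × 0.500)/50) = 0.0952. Power = Φ((0.216 − 1.96 × 0.0976)/0.0952) = about 60%.
- QD 18.5, BID 16.5: p = 0.443 and 0.666. The same formula gives about 61%.

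**3. Effect of adjustment, by simulation.** The Pearson chi-square is compared with the likelihood-ratio test for treatment in a logistic model containing baseline mean diurnal IOP.
- From the documents: 50 per arm, 2.0 mmHg, SD 3.5, baseline within 22–34 mmHg.
- Assumed: baseline mean about 25–26 and SD 1.8–2.5 after truncation; QD follow-up mean 18.5 or 20.0; correlation ρ between baseline and follow-up. No dropout is applied, because no rate is given.
- 3,000–4,000 trials per setting.

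Power for ≤18 mmHg (baseline mean 25.0, SD 1.8):

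| ρ | QD 18.5: chi-square → adjusted | QD 20.0: chi-square → adjusted |
|---|---|---|
| 0.3 | 62.9% → 64.7% | 63.5% → 65.2% |
| 0.5 | 62.6% → 69.2% | 60.0% → 67.9% |
| 0.6 | 62.4% → 73.4% | 62.2% → 71.5% |
| 0.7 | 61.6% → 79.7% | 62.4% → 78.3% |

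A wider baseline (mean 25.9, SD 2.5, QD 18.5) gives gains of 2, 6 and 10 points at ρ = 0.3, 0.5 and 0.6. Over all runs, including other assumed QD means and baseline spreads, chi-square power is about 60–66%. The gain is about 0–3 points at ρ = 0.3, 6–8 at 0.5, 9–11 at 0.6 and 15–18 at 0.7.

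SAP 3.3 does not say that its SD refers to mean diurnal IOP, which averages three readings and may vary less. With SD 3.0 (QD 18.5), chi-square power rises to about 75–76% and the gains are similar: 1–2, 6 and 10 points at ρ = 0.3, 0.5 and 0.6.

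**4. The percent-reduction endpoints.** Same model, QD 20.0, baseline SD 1.8, chi-square → adjusted:

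| ρ | ≥20% | ≥25% | ≥30% |
|---|---|---|---|
| 0.3 | 65.1% → 65.8% | 69.7% → 68.7% | 64.3% → 65.1% |
| 0.5 | 71.9% → 72.2% | 74.0% → 73.3% | 68.9% → 70.1% |
| 0.6 | 76.2% → 77.0% | 79.8% → 79.8% | 72.7% → 75.3% |
| 0.7 | 81.5% → 85.2% | 83.6% → 85.8% | 77.8% → 82.3% |

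Over all settings the gain is about −1 to +3 points up to ρ = 0.6 and 2–5 at 0.7. Baseline is already the denominator of the response, so little is left for the covariate to explain.

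**5. Validity.** With no treatment difference, both tests reject in about 5% of trials (4.7–5.9%) across the four endpoints.

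**The case against.** - **The rule is only general.** SAP 6.1 opens with the words "In general", so 8.2 may depart from it, and the protocol names the same test. This stands. A reader might infer that 6.1 and 8.2 contradict each other; the text supports only an exception without a stated reason.
- **The chi-square is valid.** Randomisation protects it, and chance baseline imbalance is already covered by its error rate. This stands. A reader might infer bias or an inflated type I error; step 5 shows neither.
- **An adjusted analysis already exists.** Mean diurnal IOP, its change and its percent change all go through the baseline-adjusted MMRM, and under SAP 6.4 superiority rests on the six IOP time points. This stands and limits the importance of the point. It does not supply an efficient estimate for ≤18 mmHg.
- **The larger gains need high correlations.** The slope of follow-up on baseline is ρ × 3.5/(baseline SD). At ρ = 0.7 it is 0.7 × 3.5/2.5 = 0.98 to 0.7 × 3.5/1.8 = 1.36 mmHg per mmHg, meaning little or no regression to the mean in subjects selected for high IOP. At ρ = 0.5 it is 0.70 to 0.97. This largely stands: the gains at 0.6–0.7 are an upper range.
- **Binary and continuous results can differ through dichotomising alone.** True. Adjustment removes one source of disagreement, not all of them.

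**Conclusion.** The point holds as one of efficiency and consistency on secondary endpoints. The responder comparisons depart from the SAP's general rule on baseline adjustment and no reason is given. The cost falls mainly on ≤18 mmHg: from almost nothing at a correlation of 0.3, through 6–8 points of power at 0.5, to 15–18 at 0.7. These figures rest on the assumed correlation, baseline distribution and QD follow-up mean, none of which the documents give.

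A reader might infer that all four responder endpoints lose material power. They do not: the three percent-reduction endpoints lose almost nothing unless the correlation is near 0.7, and for them the case is consistency only. Nor does the point touch the primary analysis, the superiority rule or the sample size.

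**What to change.** Before unmasking, amend SAP 8.2:
- Analyse ≤18 mmHg at each visit by logistic regression with treatment and baseline mean diurnal IOP.
- Report the standardised (marginal) BID versus QD risk difference with 95% CI and p-value.
- Keep the raw responder rates and the chi-square test as supportive.
- Optionally treat the percent-reduction endpoints in the same way, for consistency with 6.1. If they stay unadjusted, say so in 6.1 and give the reason.
- Record the change from protocol 9.3.6.2.

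The cost is a few lines of text and one extra model, with no new data. The model's odds ratio is conditional on baseline and not directly comparable with the raw rates, which is why the standardised risk difference should be the quoted estimate.
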